5.2. Secondary Endpoints

The following secondary endpoints will be evaluated:

- Adverse events (type and frequency) for all adverse events will be compared for the investigational and control groups
- 24-week revision rate where revision is defined as removal of any component for any reason.
- 24-week reoperation rate is defined as secondary surgery at the fracture site(s) for any reason
- Clinical Outcomes
 - o SF-12
 - Harris Hip Score
 - o EQ-5D
- Radiographs: incidence of complications such as loosening or cut-out that require reoperation or revision

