5.3 Safety

An overall summary of adverse events (AE) will be provided, including for each group the number and the percent of subjects with all AE, all serious AE, all related AE, and all AE by severity. In addition, all adverse events, serious, and non-serious adverse events will be summarized and tabulated by preferred term, both overall and by severity, by time period of onset, and by operative site

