8.1. Anticipated Adverse Events

There are immediate post-operative events that are changes from the baseline condition of the Subject, but are expected events resulting from the surgery. If these events occur, they should be recorded in the Subject's medical record and reported forward as AEs to the study sponsor.

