8.2 Adverse Events

An adverse event (AE) is any untoward medical occurrence, unintended disease or injury, or untoward clinical signs (including abnormal laboratory findings) in subjects, users or other persons, whether or not related to the investigational medical device.

At each evaluation of the subject enrolled in a clinical investigation, the investigator determines whether any adverse events (AE) have occurred, and determines their relationship to the study devices or procedure.

All adverse events, study device malfunctions and other product issues must be recorded in the medical records and entered into CRFs.

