7.1 Demographic indicators and other baseline indicators

Demographic data include gender, age, height, weight and BMI; other baseline indicators include the subject's medical history, SF-12v2 questionnaire, EQ-5D questionnaire and preoperative fracture status.

Where:

Age = (Date of informed consent - Date of birth)/365.25;

BMI = Body weight $(kg)/(\text{Height }(m))^2$.

The indicators in this part are mainly descriptive. Enumeration data are described by frequency and composition ratio, while measurement data are described by mean, standard deviation, median, quartile, maximum and minimum. The likelihood ratio Chi-square test will be used to compare the enumeration data between groups. Fisher's exact probability test will be used when the theoretical frequency in the fourfold table is less than 5.

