7.4 Secondary endpoints

Secondary endpoints include the safety and effectiveness results, imaging outcomes and adverse events.

(1) Adverse events (type and frequency) for all adverse events will be compared for the study and control groups

Calculation principle: Based on the collected adverse events in the CRF, if the subject has had at least one adverse event, it will be regarded as 'Yes'; otherwise, it will be 'No'.

The indicators in this part are mainly descriptive. Statistical analysis methods are the same as those in 7.1.

(2) 24-week revision rate, where revision is defined as any component removal for any reason.

Calculation principle: Based on the collected adverse events in the CRF, if the measure taken for the implant is filled as "Revision" and the difference between the date of occurrence of the event and the date of the operation is \leq 196 days, the revision is determined as "Yes"; if postoperative 24-week follow-up is failed, it is determined as "Missing"; others are determined as 'No';

The indicators in this part are mainly descriptive. Statistical analysis methods are the same as those in 7.1.

(3) 24-week re-operation rate, where re-operation is defined as secondary operation of the fracture site for any reason.

Calculation principle: According to the AEs in CRF. If AE "re-operation" site collected in the CRF and occurrence of the event and the date of the operation is \leq 196 days, it is determined as 'Yes'; if postoperative 24-week follow-up is failed, it is determined as 'Missing'; others are determined as 'No'.

The indicators in this part are mainly descriptive. Statistical analysis methods are the same as those in 7.1.

- (4) Clinical outcomes
- ➤ SF-12
- Harris Hip Score
- ► EQ-5D

Calculation principle for SF-12 Score:

SF-12 v2 Questionnaire (each item consists of 8 parts: body functions, physical conditions, body pain, general health, mental health, emotional conditions, social functions and vitality) and general physical and mental health assessment.

Calculation principle: SF-12 scores will be calculated by special software, and statistical analysis will be performed using "_NBS" variable.

The indicators in this part are mainly descriptive. The descriptive analysis results of the SF-12 score and the change from baseline at each follow-up will be given. The statistical analysis method is the same as 7.1. At the same time, the 95% confidence interval of the mean value of change value from each group, the

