Site No.	Random No.	Group	Age	Gender	Name of AE (SOC code)	Name of AE (PT code)	Time of postoperative occurrence (day)	Remission time (day)	Severity	Measures taken	Outcome	Correlation with the surgery	Correlation with the investigational device	Withdrawal from the trial due to AEs	Whether it is UADE	Whether it is device failure	Whether it is SAE
XXX	XXX	XXX	XXX	XXX	XXX	XXX	XXX	XXX	XXX	XXX	XXX	XXX	XXX	XXX	XXX	XXX	XXX
XXX	XXX	XXX	XXX	XXX	XXX	XXX	XXX	XXX	XXX	XXX	XXX	XXX	XXX	XXX	XXX	XXX	XXX
XXX	XXX	XXX	XXX	XXX	XXX	XXX	XXX	XXX	XXX	XXX	XXX	XXX	XXX	XXX	XXX	XXX	XXX
																	

Table 79Specific description on subjects with AEs

Notes: 1. Time of postoperative occurrence (day) = Date of occurrence of AE - Date of surgery; Remission time (day) = End date of AE - Date of occurrence of AE.

Adverse event	S	tudy group	Contr	rol group
	Number of events	Number of subjects (N=XXX)	Number of events	Number of subjects (N=XXX)
Name of AE (SOC code)	XXX	XXX(XX.XX% [#])	XXX	XXX(XX.XX%)
Name of AE (PT code)	XXX	XXX(XX.XX%)	XXX	XXX(XX.XX%)
Name of AE (PT code)				
Name of AE (SOC code)	XXX	XXX(XX.XX%)	XXX	XXX(XX.XX%)
Name of AE (PT code)	XXX	XXX(XX.XX%)	XXX	XXX(XX.XX%)
Name of AE (PT code)				

Table 80Summary of AEs

Notes: 1. #: Percentage of AEs = Number of subjects suffering from AEs/Total number of subjects in the study group or the control group;

2. Investigational device: Trochanteric Fixation Nail Advanced (TFNA); control device: Proximal Femoral Nail Antirotation (PFNA-II);

145/129

Adverse event	Study group	Control group	Statistics	P value
Total number of AEs				
Number of subjects (N miss)	XXX (XXX)	XXX (XXX)	X.XXXX	X.XXXX
Yes	XXX (XX.X%)	XXX (XX.X%)		
No	XXX (XX.X%)	XXX (XX.X%)		
Event rate difference (study grow	up-control group) and	95%CI XX.X [2	XX.X; XX.X]	

Table 80Summary of AEs (continued 1)

Notes: 1. The total number of AEs refers to the number of subjects suffering from AEs, and the AEs occur in the subject at least one time, which is considered as "Yes".

2. The likelihood ratio Chi-square test or Fisher's exact probability test is used to analyze the intergroup comparison of qualitative indicators;

3. The difference of event rate and 95% confidence interval were analyzed by Wald test with continuous correction;

Table 81	Specific	description or	1 subjects v	with investigational	device-related AEs
		I I I I I I I I I I I I I I I I I I I	J		

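### Protocol 5.3 promises adverse events by preferred term and severity and by operative site; the SAP summary tables give neither, and its AE comparisons pool all locations or rest on unblinded causality judgments

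*SAP*

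**What the plan says.** **Protocol.** Section 5.3 requires all, serious and non-serious AEs to be "summarized and tabulated by preferred term, both overall and by severity, by time period of onset, and by operative site". Section 5.2 makes AEs a secondary endpoint: "Adverse events (type and frequency) for all adverse events will be compared for the investigational and control groups". The net is wide. Expected postoperative changes are to be "reported forward as AEs to the study sponsor" (8.1), and the AE definition in 8.2 covers "untoward clinical signs (including abnormal laboratory findings").

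**SAP.** Section 7.4(1) reduces the endpoint to one yes/no item per subject: "if the subject has had at least one adverse event, it will be regarded as 'Yes". Table 80 lists events and subjects by SOC and preferred term. Its continuation tests a single row, with the note that "The total number of AEs refers to the number of subjects suffering from AEs". Section 7.1 gives the test: a likelihood-ratio chi-square, except that "Fisher's exact probability test will be used when the theoretical frequency in the fourfold table is less than 5".

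**The concern.** The trial is described as comparing the safety as well as the effectiveness of two nails (Protocol 4.0). Differences between nails would show most plausibly at the operated hip: wound, implant, peri-implant fracture, local pain. Protocol 5.3 asks for a tabulation that would separate these events and grade them within each term. The SAP drops that tabulation without saying so. What remains on the AE side is a set of comparisons in which systemic events can dilute a local excess, or in which the split depends on an attribution made by people who know the arm. The primary endpoint is not affected.

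**Working it through.** **1. Protocol 5.3 against the SAP tables**

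| Asked for in Protocol 5.3 | What the SAP gives |
|---|---|
| Preferred term, overall | Tables 80, 82 (device-related), 87 (SAEs), 89 (device-related SAEs), by arm |
| Preferred term by severity | No summary table. Tables 84 and 91 give the worst severity per subject, and Tables 85 and 92 give events by severity, all pooled over terms. Severity stands beside the term only in the subject listings |
| By time period of onset | AE yes/no at each visit (Tables 54, 59, 64, 69); day of onset in the listings; not by term |
| By operative site | Nothing. The site number in Table 79 identifies the study centre |
| Non-serious AEs separately | No table |

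This mismatch needs no assumption. The protocol does not define operative site, but whether it means location on the body or operating centre, no SAP table shows AEs by it.

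**2. The plan's own sample size**

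Inputs (Protocol 10.9, SAP 6.2 and 6.6): union rate 0.95 in both arms, margin 0.10, one-sided 0.025, power 80%.

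n = (1.960 + 0.842)² × 2 × 0.95 × 0.05 / 0.10² = 74.6, so 75 per arm. 75 / 0.80 = 93.75, so 94 per arm and 188 in total. Both stated figures reproduce. The documents state no power for any AE comparison.

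**3. How far any-AE dilutes a local excess**

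Assumptions: 94 per arm; operative site read as the operated hip versus elsewhere; other AEs occur in a proportion b of subjects, equal in both arms and independent of local AEs. The documents give no b, so a range is shown.

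Any-AE rate = 1 − (1 − b)(1 − p), where p is the local rate. The difference between arms therefore shrinks to (1 − b) times the local difference. Power is by exact enumeration of the SAP's test at two-sided 5%.

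Local AEs 10% v 20%:

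| Background b | Rates compared | Power |
|---|---|---|
| direct local comparison | 10.0% v 20.0% | 48.9% |
| 10% | 19.0% v 28.0% | 31.1% |
| 30% | 37.0% v 44.0% | 15.9% |
| 50% | 55.0% v 60.0% | 10.2% |
| 70% | 73.0% v 76.0% | 7.8% |
| 85% | 86.5% v 88.0% | 6.1% |

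Other cases, direct and then through any-AE at b = 10%, 30%, 50%, 70%:

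- 5% v 10%: 26%; then 13%, 8%, 6%, 6%.
- 5% v 20%: 90%; then 63%, 31%, 17%, 11%.

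For scale, the PFNA-II complication table in Protocol 1.3.3 shows 4.3% for cut-out and 8.7% for migration. A difference of 4.3% v 8.7% has 23% power even when compared directly.

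**4. The comparisons that do not pool everything**

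Device-related AEs (Table 82 continued), device- and surgery-related events per subject (Table 83) and relatedness per subject (Table 84) are compared by arm. Relatedness is decided by the investigator (Protocol 8.2), and Protocol 7.5 says that surgeon investigators and study staff cannot be blinded. Revision and re-operation (Tables 35, 36) capture only problems that reach surgery. Table 43 covers complications needing re-operation or revision, but the rule in SAP 7.4(5) codes such cases as missing and all others as no, so as written it cannot count one.

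**The case against.** The strongest reply is that local problems are compared in several places. Each preferred term is shown by arm in Table 80, so a peri-implant fracture is not lost. Wound healing, focal tenderness, percussion pain and abnormal activity are tested at every follow-up visit (Tables 57, 62, 67, 72), as are implant status, reduction and need for re-operation (Tables 58, 63, 68, 73). Table 82 (continued) would match the direct local comparison if local problems are rated at least possibly related. Protocol 5.3 asks for tabulation rather than testing, and SAP 7.4 treats the AE indicators as mainly descriptive.

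All of this stands, and it rules out a stronger reading. A reader might infer that the SAP's safety comparison has almost no power, so that a doubling of local complications would go unseen. The documents do not support that. It ignores the tables just listed, and it needs a high background AE rate that neither document gives. The wide AE definition makes a high rate plausible but does not establish one.

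Two further replies stand in part. Operative site is undefined, and with single-limb enrolment (Protocol 6.1) the phrase could be template text or mean the centre; the SAP should settle this. A coder blind to arm would still be classifying reports from unblinded investigators, so the added row lessens the dependence on judgment but does not remove it. None of this closes the gap against Protocol 5.3.

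**Conclusion.** The concern holds as a gap between protocol and SAP with a moderate consequence. No SAP summary table gives preferred term by severity or anything by operative site, and this is a matter of record. The loss of sensitivity is conditional. For local AEs of 10% v 20%, power falls from 49% directly to between 31% and 6% through any-AE, on assumed backgrounds of 10% to 85%, equal in both arms and independent of local events, and on reading operative site as the operated hip. The AE comparisons that avoid this dilution depend on unblinded causality.

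A reader might also infer that adding the operative-site row would make safety adequately powered. It would not: 5% v 10% local has 26% power directly. The gain is the promised tabulation and an interval estimate for local events that does not depend on attribution to the device.

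**What to change.** 1. Define operative site in the SAP. The reading used here is the operated hip versus elsewhere.
2. Split the SOC/preferred-term tables (80 and 87) into mild, moderate and severe. Severity is already recorded for each event, so this is programming only.
3. In Tables 80 (continued) and 87 (continued), add the number of subjects with at least one operative-site AE or SAE, with the difference and 95% CI, labelled as descriptive.
4. If the AE form has no location item, set a flag from the verbatim and preferred terms, blind to arm, before database lock, and show it in Table 79.
5. For the rest of the Protocol 5.3 sentence (onset period by term, and non-serious AEs), either add the tables or state and justify the departure.

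The cost is SAP wording, some coding time and a few borderline location decisions. No new data collection is needed.

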4.0 STUDY DESIGN

This is a prospective, multicenter, randomized, controlled, two-arm, non-inferiority study which will be conducted in China, comparing the safety and the effectiveness of two intramedullary nails (the investigational group is TFNA and the control group is PFNA-II). Patients enrolled at each site will be randomized in a ratio of 1:1, i.e. one patient assigned to surgery implanted with TFNA for each patient assigned to PFNA-II. Separate block randomization schedules within each site will be used to ensure equal distribution of treatment and control patients. Up to 15 centers will be approved to participate in this study.

Patient will be clinically followed after surgery at 1, 6, 12 and 24 weeks. The data up to and including 24 week follow up visit will be used in determining the primary safety and effectiveness of the TFNA.

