6.2 Sample size calculation

The sample size calculation is determined based on the primary endpoint using PROC POWER in SAS software version 9.3. It assumes that the fracture union rate at 24 weeks after surgery in the TFNA group would be equivalent to that of the PFNA-II group, and a common fracture union rate is approximately 95% or greater based on the literature review. With a non-inferiority margin of 0.10 and a power of 80%, this implies a sample size of 75 for the TFNA and of 75 for PFNA-II surgery groups, respectively. The sample size will be increased to 188 (94 per group) to accommodate potential 20% attrition.

The sample size applies to patients enrolled, randomized, and actually treated. Some patients who enroll in a study and are randomized may not be ultimately treated for various reasons. Patient enrollment and randomization will continue until the proposed sample size for treated patients is complete.

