6.3 Analysis population

Full Analysis Set (FAS): The set of subjects determined following the intent-totreat (ITT) principle refers to the data set constituted by all subjects who participate in the randomized study and receive the investigational product (implant) (i.e., ITT population defined in the protocol).

Per Protocol Set (PPS): Refers to the subgroup of treatment population who completes the trial and excluded the population that seriously violates the protocol (which means that study subjects violating the inclusion criteria or meeting exclusion criteria, loss to follow-up during the trial, cross enrollment, out-of-specification use of investigational products, out-of-window time, etc.).

Safety Set (SS): Set of all subjects who participate in the study and use the investigational products and undergo at least one safety evaluation after baseline. (The definitions of SS and FAS are the same. Therefore, SS is not defined separately).

Actual Treatment Set (ATS): All patients who participate in the randomized grouping, complete the trial, actually receive the scheduled treatment in the study (not necessarily consistent with the results of randomized grouping) and do not seriously violates the protocol. On the basis of PPS, only cross-enrolled patients are included, but they are then grouped and analyzed according to their actual treatment, i.e., the actual treatment set is formed.

The primary efficacy analysis will be based on FAS, PPS and ATS (if applicable). All baseline demographic data and secondary efficacy indicator analysis will be performed on the basis of FAS, and the safety evaluation will be performed on the basis of FAS.

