6.6 Significant level and statistical analysis software

For the primary endpoint, statistical analysis will be performed at the one-sided 0.025 significance level (corresponding to the one-sided confidence limit of the 95% confidence interval). For other endpoints, all statistical analysis will be performed at the two-sided 0.05 significance level (except for special instructions). SAS[®] 9.4 statistical software will be used for statistical analysis.

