(2) Continuous correction Newcombe-Wilson for non-adjusted central;

The result from test (1) will used for the primary analysis result, the result from test (2) will be used as sensitivity analysis result. If the lower limit of the bilateral two-sided 95% confidence interval on differences in efficacy between the study group and the control group (equal to the lower limit of unilateral 95% confidence interval) is greater than -10%, it can be considered that the investigational product is not inferior to the control product

If the actual study results show that other baseline variables (such as age and gender) are significantly different between the study group and the control group, it will be fully communicated to the investigator in the data analysis stage. Based on the results of univariate analysis for baseline variables and primary endpoint, previous literature references and the clinical expert experience, the indicators affecting the primary endpoint to cause imbalance between groups, i.e., confounding factors, will be further specified. These indicators will be considered into the generalized linear model for correction and included into the sensitivity analysis of the primary endpoint analysis.

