Investigational related SAE	device-	Study group	Control group	Statistics	P value
Total number of investigational dev related SAEs Number of subjects Yes No		XXX (XXX) XXX (XX.X%) XXX (XX.X%)	XXX (XXX) XXX (XX.X%) XXX (XX.X%)	X.XXXX	X.XXXX
Event rate difference	e (investigat	ion group-control gr	oup) and 95%CI	XX.X [XX.X; X	[X.X]

Table 89 Summary of investigational device-related SAEs (continued)

Notes: 1. The total number of investigational device-related SAEs refers to the number of subjects suffering from investigational device-related SAEs and the investigational device-related SAEs occur in the subject at least one time, which is considered as "Yes".

2: Investigational device-related SAEs refer to those "definitely related", "probably related" and "possibly related" with the investigational device;

3. The likelihood ratio Chi-square test or Fisher's exact probability test is used to analyze the intergroup comparison of qualitative indicators;

4. The difference of event rate and 95% confidence interval were analyzed by Wald test with continuous correction;

Table 90 Summary of SAEs (Number of events per subject)

Indicator	Study group (N=XXX [#]	(N=XX)	K ^{#1}) P
Total number of advers			
	$XXX ^{\#2}(XX.X^{3})$	$XXX^{\#2} (XX.X^{\#3})$	X.XXXX
	Event difference (study group-con	trol group) and 95%C XX.	X [XX.X; XX.X]
Total number of device	e related adverse events XXX ^{#2} (XX.X ³)	XXX ^{#2} (XX.X ^{#3})	X.XXXX
Ev	ent rate difference (study group-con	ntrol group) and 95%CI XX.	X [XX.X; XX.X]
Total number of surger	ry related adverse events XXX ^{#2} (XX.X ³)	XXX ^{#2} (XX.X ^{#3})	X.XXXX
Ev	ent rate difference (study group-con	ntrol group) and 95%CI XX.	X [XX.X; XX.X]
related" or "o 2. Surgery rela related" or '	lated adverse events are the adverse definitely related" to the study devic ated adverse events are the adverse 'definitely related" to surgery; umber of subjects; #2: Total num	ces; events that are "probably related"	-

#3: Total number of events/total number of patients: the average number of events per subject;

- 4. Group t-test is used to analyze Event rate difference (study group-control group) and 95%CI
- 5. Investigational device: Trochanteric Fixation Nail Advanced (TFNA); control device: Proximal Femoral Nail Antirotation (PFNA-II);

Indicator	Study group control g	group statistic	Р	
Severity				
NO. (Nmiss)	XXX (XXX)	XXX (XXX)	X.XXXX	X.XXXX
mild	XXX (XX.X%)	XXX (XX.X%)	
moderate	XXX (XX.X%)	XXX (XX.X%	%)	

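### The continuity-corrected Wald intervals in the SAP safety tables have no sparse-count fallback: 0 v 0 events at 94 per arm would print only ±1.06 points, and coverage can fall well below 95% when one arm's true rate is near zero

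*SAP*

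**What the plan says.** The SAP reports a difference in event rates with a 95% interval in five safety summaries, and the note is the same each time: "The difference of event rate and 95% confidence interval were analyzed by Wald test with continuous correction". It stands under the continued parts of Table 80 (any AE), Table 82 (device-related AEs), Table 87 (SAEs), Table 89 (device-related SAEs) and Table 94 (UADEs). For the number of events per subject, note 4 to Tables 83 and 90 says: "Group t-test is used to analyze Event rate difference (study group-control group) and 95%CI".

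Outside the primary endpoint, SAP 6.6 sets the level: "all statistical analysis will be performed at the two-sided 0.05 significance level". On the analysis set, SAP 6.3 says "the safety evaluation will be performed on the basis of FAS". SAP 7.1 switches to Fisher's exact test for small expected counts, but that governs the P value and not the interval. The SAP does name a score-type interval, for the primary-endpoint sensitivity analysis in 7.3: "Continuous correction Newcombe-Wilson for non-adjusted central".

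**The concern.** The Wald standard error is built from the observed proportions, so an arm with no events contributes nothing to it. With no events in either arm, only the continuity correction is left, and that depends on sample size alone. A table showing 0/94 v 0/94 would then carry a nominal 95% interval of about one point either way, although 94 patients cannot rule out a rate of nearly 4%.

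The report supports registration in China of a nail whose alloy has not been used there for a similar application. A reader looking for rare device harm would turn to the sparse tables, and there the interval would be falsely tight. The t interval in Tables 83 and 90 has the same flaw in starker form: if every subject has zero events, both variances are zero and the interval has no width.

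**Working it through.** **Inputs.** Allocation is equal (Protocol 4.0: "Patients enrolled at each site will be randomized in a ratio of 1:1"). On size, SAP 6.2 says: "The sample size will be increased to 188 (94 per group) to accommodate potential 20% attrition". It adds: "The sample size applies to patients enrolled, randomized, and actually treated". The true event rates are my assumption.

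**The plan's own figure.** (1.960 + 0.842)² × 2 × 0.95 × 0.05 / 0.10² = 74.6, so 75 per arm; 75/0.80 = 93.75, so 94 per arm and 188 in total. This reproduces the SAP. I use n = 94 per arm.

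**Interval limits.** Corrected Wald: d ± [1.96 × √(p₁q₁/n + p₂q₂/n) + (1/n + 1/n)/2]. The correction is 1/94 = 0.01064.

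- 0 v 0: the standard error is 0, so ±1.06 points. With 75 per arm it would be ±1/75 = ±1.33.
- 1 v 0: d = 0.01064, SE = 0.01058; upper limit 0.01064 + 0.02074 + 0.01064 = 4.20%.
- 2 v 0: d = 0.02128, SE = 0.01488; upper limit 0.02128 + 0.02917 + 0.01064 = 6.11%.

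Newcombe-Wilson: when the second arm has no events, the upper limit for the difference is the Wilson upper limit of the first arm. At 0/94, uncorrected, that is z²/(n + z²) = 3.841/97.841 = 3.93%.

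| Events | Wald, corrected | Newcombe-Wilson, uncorrected | Newcombe-Wilson, corrected |
|---|---|---|---|
| 0 v 0 | ±1.06 | ±3.93 | ±4.89 |
| 1 v 0, upper limit | 4.20 | 5.78 | 6.62 |
| 2 v 0, upper limit | 6.11 | 7.43 | 8.21 |

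As a yardstick, the exact one-arm upper limit for 0/94 is 1 − 0.025^(1/94) = 3.85%.

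**Coverage.** This is exact, by full enumeration of two independent binomials with n = 94. If the true difference exceeds 1.06 points, every 0 v 0 result misses it. With the other arm at 0%, in the first three cases below, that outcome accounts for almost all of the shortfall.

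- 1.1% v 0%: 0.989^94 = 35.4% chance of 0 v 0; coverage about 65%.
- 1.5% v 0%: 0.985^94 = 24.2%; coverage 75.8%.
- 2% v 0%: 0.980^94 = 15.0%; coverage 85.0%.
- 2% v 0.5%: 0.980^94 × 0.995^94 = 9.3%; coverage 90.4%, the rest of the shortfall coming from other counts.
- 2.5% v 0%: 90.7%. 3% v 0%: 94.2%.

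Away from that region the interval is sound or conservative: 99.6% at 2% v 2%, 96.3% at 3% v 1%, 96.9% to 100% over equal rates from 0 to 10%, and a minimum of about 95.0% when both rates are at least 1%. If the true difference is under 1.06 points, coverage is about 100%.

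Uncorrected Newcombe-Wilson covers at least 99.6% at 1.5% v 0%, 2% v 0% and 2% v 0.5%.

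**The case against.** The strongest reply is that these intervals decide nothing. No safety hypothesis or margin rests on them. The same tables show counts and denominators, exact tests are available for the P value, and listings describe every event. That is true and limits the consequence, but an interval labelled 95% should still be close to 95%.

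The second reply is that the failure is narrow, and this stands. Under-coverage needs one arm near zero and a true difference of roughly 1.1 to 2.5 points. A reader might infer that the SAP's safety intervals are too narrow in general; the coverage results do not support that.

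Third, a reader might take the flaw to bite equally in all five tables. Table 80 counts any AE, and Protocol 8.1 wants even expected post-operative events reported. SAEs (Table 87) include death and in-patient or prolonged hospitalisation, in a fracture population that Protocol 1.1 describes as predominantly elderly. Sparse counts are less likely in both. Nor do the documents show that device-related SAEs will be few. SAP 7.7 counts possibly related events, and Protocol Table 4 gives PFNA-II reoperation as 6.5% and cut-out as 4.3%. If all such events were rated device-related, 94 × 0.043 = 4 to 94 × 0.065 = 6 events per arm would follow. On the other side, the same table shows later femur fracture at 0.0% v 2.2%, so a near-zero arm against about 2% is not fanciful. UADEs are the clearest sparse case.

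Finally, Newcombe-Wilson over-covers in these sparse cases. That is a real cost in width, but it errs on the cautious side.

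**Conclusion.** The notes are wrong as written for sparse counts, chiefly in Table 94, then Tables 89 and 82. At 0 v 0 the printed interval is ±1.06 points where a score-based interval gives ±3.93 or ±4.89. Under the assumed rates above, coverage falls to between about 65% and 91%. The widths depend only on 94 per arm; the coverage figures also depend on true rates that the documents do not supply.

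Two further inferences are not supported. The non-inferiority conclusion is untouched, because the primary analysis does not use this method. And the revision, reoperation and complication tables (35, 36 and 43) plan no interval, so they do not share the error; adding one there would be a preference.

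**What to change.** In the notes to Tables 82, 89 and 94, and for consistency Tables 80 and 87, replace the Wald interval by a Newcombe-Wilson interval and state whether it is continuity-corrected. SAP 7.3 names the corrected form (±4.89 at 0 v 0); the uncorrected form (±3.93) already covers at least 99.6% in the three sparse cases checked. Either is defensible if chosen in advance.

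In Tables 83 and 90, do not report the t interval when both arms have no events. Zero events in one arm alone does not give zero width, so the rule need not go further.

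The cost is a change of table notes before database lock, using a type of interval that the SAP already plans for the primary endpoint. The price is wider, conservative safety intervals.
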